3 INVESTIGATIONAL PLAN

This is a multi-center, uncontrolled observational study of patients who at the time of entry were prescribed with HUMIRA®(adalimumab) following normal clinical practice, with or without other anti-rheumatic treatments, prior to enrollment in this study.

Patients will be followed for 5 years within the post-marketing observational study.

Physicians will be provided with a study kit that includes a protocol, patient informed consent forms, adverse event report forms, and Data Report Forms (DRFs), for each patient to be enrolled. The participating physician will already have provided a prescription to the patient for HUMIRA®(adalimumab), along with instructions for appropriate use according to the European Union (EU) Summary of Product Characteristics (SPC).

Once the physician has determined that the patient meets the inclusion criteria, and the patient has agreed to be included in the observational study, the patient's baseline demographic data, and disease status will be reported in the Baseline DRF. The physician will then follow-up the patient via regular office visits at intervals as determined by routine clinical practice or as recommended by national guidelines.

Patient's safety and efficacy data if they are part of clinical routine will be recorded in the DRFs at Baseline, and regular visits which are closest to Month 3, Month 6, Month 9, Month 12, Month 18, Month 24, Month 30, Month 36, Month 42, Month 48, Month 54, and Month 60. While the physician will likely deem it appropriate and necessary to have the patient return for intermediate visits during the study period, data will be collected via DRFs only at the intervals which correspond closely to those described above. Physicians are encouraged to treat their patients as they would in their routine clinical practice. If treatment with HUMIRA®(adalimumab) is permanently discontinued for any reason, patients will be discontinued from the study and the reason should be recorded. Physicians will be asked to record adverse events up to 3 months after last administration of HUMIRA®(adalimumab) on the DRF of the next scheduled data collection time.

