1. METHODOLOGY

The purpose of this statistical analysis plan is to provide detailed information on the statistical analysis of the data of the ProAct study. The plan is based on the quotation dated 18 October 2017 and the mail dated 4 April 2017.

1.1 *Study Objective*

To evaluate the effectiveness and safety of adalimumab for the treatment of rheumatoid arthritis (RA), psoriatic arthritis (PsA) and ankylosing spondylitis (AS) in real life clinical practice.

1.2 *Available data*

The questionnaires table, as received on 5 February 2018, contained 47378 records, of which 5947 baseline visits. This database has been adapted by hardcoding in the programmation in order to resolve inconsistencies, double patients, misclassification of visits, add additional visit CRF pages, add additional AE pages. A total of 5920 patients of which 2836 rheumatoid arthritis patients, 1127 psoriatic arthritis patients (of which 197 Oligoarticular PsA) and 1957 ankylosing spondylitis patients were included in the analysis.

The parameter DAS28 was entered in the database from the moment the new Belgium reimbursement criteria for Humira were in place (2010).

Visits were scheduled at baseline, months 3, 6, 9 and 12, then every 6 months till 5 years.

1.3 *Patient Population*

All patients are to be considered in the analysis.

1.4 *Data Handling*

All data handling rules used during the analysis will be described in the section Methodology of the Statistical Report.

‘LT’ visits are visits added in the database for patients who were lost to follow-up in order to close the patient in the database. These visits will not be taken into account for any analysis.

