1.5 Derived Data

- Study duration (year) = (visit date of last visit – visit date of baseline visit)/365.25

- Completed patients: patients with ≥ 1734 days study duration

- Treatment duration (year):

For completed patients:

(Date of last visit – Date of baseline visit)/365.25

For not completed patients:

Sum of number of weeks/52, months/12 and years patient has been on drug documented on the last visit

If missing: (Date of last visit – Date of baseline visit)/365.25

Note: Some patients stopped Humira temporally. The periods of not taken Humira are not taken into account for the analysis. These patients will be considered as having taken Humira during the complete study.

- Treatment duration category:

0 to 3 months

> 3 to 6 months

> 6 to 9 months

> 9 to 12 months

> 12 to 18 months

> 18 to 24 months

> 24 to 30 months

> 30 to 36 months

> 36 to 42 months

> 42 to 48 months

> 48 to 54 months

> 54 to 60 months

> 60 months

- For the purpose of the analysis of the evolution of parameters over time, follow-up visits will be classified into time windows, defined upon the number of days between Visit 1 and the date of each subsequent visit (PERIOD = Date of follow-up visit - Date of Visit 1)

- Period = Date of visit – Date of baseline visit

- Month 3 window: $1 \leq \text{period} \leq 137$ days

- Month 6 window: $138 \leq \text{period} \leq 228$ days

- Month 9 window: $229 \leq \text{period} \leq 319$ days

- Month 12 window: $320 \leq \text{period} \leq 456$ days

- Month 18 window: $457 \leq \text{period} \leq 639$ days

- Month 24 window: $640 \leq \text{period} \leq 821$ days

- Month 30 window: $822 \leq \text{period} \leq 1004$ days

- Month 36 window: 1005 <= period <= 1186 days
- Month 42 window: 1187 <= period <= 1368 days
- Month 48 window: 1369 <= period <= 1551 days
- Month 54 window: 1552 <= period <= 1733 days
- Month 60 window: 1734 <= period <= 1916 days

Each visit will be classified in a time window. If the date of the visit is completely missing, it will be assumed that the visit took place on the target day of the window as indicated on top of the follow-up page. If more than one follow-up visit is classified into the same time window, the visit closest to the target day is retained. If within a time window there are two visits at the same distance from the target day, the visit which comes first (e.g. before the target date) is retained. If there are two visits on the same date, the first record is retained.

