- BASDAI responder: a relative improvement in BASDAI of $\geq 50\%$
- DAS28 category: <2.6 , ≥ 2.6 and ≤ 3.2 , >3.2
- Serious adverse event = event where at least one criteria of seriousness is present
- An adverse event is considered to start in a certain year if the difference between start date and date of baseline (=AEPER) is in the following windows:
 - Year 1: $0 \leq \text{AEPER} < 365.25$
 - Year 2: $365.25 \leq \text{AEPER} < 730.5$
 - Year 3 $730.5 \leq \text{AEPER} < 1095.75$
 - Year 4: $1095.75 \leq \text{AEPER} < 1461$
 - Year 5: $1461 \leq \text{AEPER} < 1826.25$

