 - 1.7.4 Number of DMARDs Used
 - 1.7.5 Frequency of Use of Each Type of DMARD
 - 1.7.6 Combination of Types of DMARD Used
 - 1.8 Study Duration
 - 1.9 Results of the Tests

- 2 Follow-up Data**
 - 2.1 Treatment Duration
 - 2.1.1 Treatment Duration
 - 2.1.2 Treatment Duration Category
 - 2.1.3 Treatment Duration Broken Down by Year of Start Treatment
 - 2.1.4 Treatment Duration Broken Down by DAS28 Category at Window 2 (Month 6)
 - 2.2 Physician's Assessment of Disease Activity
 - 2.2.1 Physician's Assessment of Disease Activity in Each Window
 - 2.2.2 Physician's Assessment of Disease Activity - Difference from Baseline
 - 2.3 Clinical Examination
 - 2.3.1 Joint Assessment (tender joints count, swollen joints count) in Each Window
 - 2.3.2 Joint Assessment (tender joints count, swollen joints count) – Difference from Baseline
 - 2.3.3 Inflammatory Parameters (CRP, ESR) in Each Window
 - 2.3.4 Inflammatory Parameters (CRP, ESR) – Difference from Baseline
 - 2.3.5 Physical Function (HAQ %) in Each Window
 - 2.3.6 Physical Function (HAQ %) – Difference from Baseline
 - 2.3.7 Physical Function (HAQ %) - Number of Patients with >7.33% Reduction from Baseline
 - 2.3.8 DAS28 in Each Window
 - 2.3.9 DAS28 – Difference From Baseline
 - 2.3.10 DAS28 Category in Each Window

3 Adverse Events

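### Table 2.1.4 groups treatment duration by a Month 6 DAS28 that may have been measured after adalimumab was already stopped

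*SAP*

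**What the plan says.** SAP section 2 lists table 2.1.4, "Treatment Duration Broken Down by DAS28 Category at Window 2 (Month 6"), for RA, PsA and AS alike. The categories, in SAP 1.5, are below 2.6, 2.6 to 3.2, and above 3.2. The Month 6 window is days 138 to 228 after baseline.

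On which visits count, SAP 1.5 states: "Each visit will be classified in a time window". The one exclusion is in SAP 1.4, for LT visits added to close patients lost to follow-up: "These visits will not be taken into account for any analysis". No on-treatment condition is attached to the window or to the table.

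Treatment duration in SAP 1.5 has two definitions. For completed patients, and for others when the entry is missing, it is last visit minus baseline visit. For the remaining non-completed patients it is "Sum of number of weeks/52, months/12 and years patient has been on drug documented on the last visit", with no stated starting point.

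Protocol section 3 says that on permanent discontinuation "patients will be discontinued from the study and the reason should be recorded". It also asks for adverse events up to three months after the last dose on the following scheduled form. Protocol 3.3.7 requires an Early Termination form at withdrawal. Protocol 3.1.1 enrols patients already on adalimumab.

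**The concern.** A table that sorts a duration by a later measurement makes sense only if the patient was still at risk of the outcome when the measurement was made. Here a patient can stop the drug, be seen afterwards within days 138 to 228, and be placed in a DAS28 category by that visit. The treatment duration was fixed before the category existed, so any association from such patients runs backwards: stopping, or what followed it, sets the category.

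This is the only listed table that crosses on-treatment disease activity with treatment duration. Its layout invites the reading that good control at Month 6 goes with longer persistence. If patients who had already stopped tend to have high DAS28, they add very short durations to the group above 3.2, and the table shows that pattern whether or not it is true.

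**Working it through.** The plan gives no expected duration, retention or DAS28 distribution for this table, so there is no planned figure to reproduce. The window itself checks: the midpoints between targets are 4.5 × 30.4375 = 137.0 days and 7.5 × 30.4375 = 228.3 days, which reproduces 138 to 228.

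**Can the DAS28 follow the stop?** The adverse-event rule in Protocol section 3 and the Early Termination form in 3.3.7 make a form at or after the stop foreseeable. SAP 1.4 drops only LT visits, so such a form is windowed. Keeping the visit closest to the target day does not help when it is the only one in the window. A hypothetical case: the patient stops on day 120 and is seen on day 150 with DAS28 4.5. The category is above 3.2, and time on drug since baseline is 120/365.25 = 0.33 year.

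**How large could the effect be?** Suppose that, among patients on drug at the visit, DAS28 is unrelated to later stopping. Let *s* be the share of Month 6 DAS28 values from patients who had already stopped, and M_on and M_off the mean durations of on-drug and stopped patients. The spurious difference in mean duration, below 2.6 minus above 3.2, is

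D = (M_on − M_off) × (s_H − s_L),

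where s_H and s_L are the stopped shares within the high and low categories.

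Assumptions, none from the documents:
- on-drug categories (low/middle/high) 40/15/45%
- stopped patients 15/10/75% (higher), 40/15/45% (same) or 60/15/25% (lower)
- stops between day 91 and the visit, with 50% or 100% of those patients having a Month 6 DAS28
- five-year retention 35% to 70%
- first-year stopping hazard 1 or 2 times the average
- duration capped at 5 years

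Worked case (50% retention, constant hazard, *s* = 3.4%, stopped patients higher):
- hazard = ln 2 / 5 = 0.1386 per year
- M_on = 0.5 + (1 − e^(−0.1386 × 4.5)) / 0.1386 = 3.85 years
- M_off ≈ (0.25 + 0.5) / 2 = 0.375 year
- s_H = 0.034 × 0.75 / (0.034 × 0.75 + 0.966 × 0.45) = 0.0554
- s_L = 0.034 × 0.15 / (0.034 × 0.15 + 0.966 × 0.40) = 0.0130
- D = 3.475 × 0.0424 = 0.147 year, against 0.147 by simulation

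Simulated results (2,000,000 patients per scenario, stopped patients higher):

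| Five-year retention | First-year hazard vs average | Stopped patients with a Month 6 DAS28 | *s* | Mean difference (years) | Median difference (years) |
|---|---|---|---|---|---|
| 70% | 1 | 50% | 0.9% | 0.04 | 0 |
| 50% | 1 | 100% | 3.4% | 0.15 | 0 |
| 50% | 2 | 100% | 6.7% | 0.27 | 0 |
| 35% | 2 | 100% | 10.0% | 0.34 | 0.81 |

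**Direction.** With the same DAS28 distribution in stopped and on-drug patients, the difference is 0.00 year. With lower DAS28 in stopped patients, it is −0.11 year at *s* = 3.4% and −0.20 year at *s* = 6.7%.

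**Is the baseline origin a cause?** The 0.00 above arises with duration counted from baseline. Excluding patients who stopped at or before the visit leaves at most 0.005 year in these scenarios, whether duration runs from baseline or from the visit. The exclusion does the work. With no stopped patients, the baseline origin creates a gap only if visit day differs by category: 0.12 year at the extreme where every low patient is seen on day 228 and every high patient on day 138.

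**The case against.** The strongest reply is that a post-stop DAS28 is only a possibility. Patients who stop permanently leave the study, the three-month rule covers adverse events only, Table 1 of the protocol schedules no separate efficacy assessment at termination, and the content of the Early Termination form is not visible. This stands as a limit on size: the number affected may be small. It does not remove the gap in the rule, because nothing in the SAP excludes such a value if one was recorded.

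The analysis is also descriptive. Protocol section 5 rules out inferential techniques, and the SAP attaches no test or predictive claim to this table. That stands too: the risk is misinterpretation, not a type I error. Medians may not move at all where at least half of each group reaches the cap.

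A reader might infer three stronger points that the documents do not support.
- *That counting duration from baseline favours the low group.* Every categorised patient has a visit in days 138 to 228, so the guaranteed early time is shared by all three categories. Baseline is also the stated origin only for completed patients and the missing-entry fallback.
- *That low activity is bound to look better.* This requires higher DAS28 in stopped patients, which is plausible where loss of response drives stopping but is stated nowhere.
- *That a high DAS28 at the visit where the drug is stopped is equally an artefact.* If that finding prompts the stop, it is a genuine link between Month 6 activity and shorter treatment. An illustration that treats stop and post-stop visits together (2% to 10% of values, 70% to 100% of them above 3.2, 40% of other patients above 3.2, stop hazard 0.15 per year) gives 0.08 to 0.73 year. It sets the true association to zero by assumption, so it cannot be read as bias.

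**Conclusion.** The point holds in a limited form. Table 2.1.4 lets a DAS28 taken after the stop define the group, so the outcome can precede its supposed predictor. With no true association, the mean difference could be about 0.04 to 0.34 year in favour of low Month 6 activity if patients who had already stopped have higher DAS28. It is zero if their DAS28 is the same, and reversed if lower. The range rests on the assumed retention, stopping pattern and category shares listed above; the documents supply none of them.

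A separate ambiguity should be settled at the same time. The SAP mixes time origins within one table: baseline for some patients, and documented time on drug with no stated origin for others, in a study whose patients enter on ongoing treatment. This is a change that should be made, not a flaw that undermines the study.

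**What to change.** In each indication, restrict table 2.1.4 to patients with a Month 6 DAS28 who were still on adalimumab at that visit. Tabulate remaining treatment duration from that visit, with one stated origin for all patients. On separate lines, by DAS28 category, give the number who had stopped before the visit and the number who stopped at it, so that both stay visible and are not confused.

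The visit is a better landmark than the end of the window (day 228). A patient assessed on day 140 who stops on day 200 was properly measured before the outcome and should stay in. Moving the origin to the visit is for clarity, since all tabulated time then follows the assessment. It shortens every group by about 0.5 year and does not change the contrast unless visit day differs by category; in the extreme timing case above it would give −0.13 year instead of 0.12. Showing the visit day by category would settle this.

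The cost is a slightly smaller table and a short derivation of on-drug status at the visit. The SAP defines no stop date, so this needs a stated rule, including how temporary interruptions are treated. SAP 1.2 shows that the data were received on 5 February 2018, so the number affected can be counted once on-drug status is derived.

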3.1 Adverse Events

3.1.1 Patients with Adverse Events, Patients with Serious Adverse Events, Patients with Fatal Adverse Events and Patients with Adverse Events Causing Treatment Discontinuation

3.1.2 Patients with Adverse Events by MedDRA System Organ Class

3.1.3 Patients with Adverse Events by MedDRA System Organ Class and Preferred Term

3.2 Adverse Events per Year

3.2.1 Patients with Adverse Events, Patients with Serious Adverse Events, Patients with Fatal Adverse Events and Patients with Adverse Events Causing Treatment Discontinuation

3.2.2 Patients with Adverse Events by MedDRA System Organ Class

3.2.3 Patients with Adverse Events by MedDRA System Organ Class and Preferred Term

3.3 Adverse Events by Cumulative Yearly Period

3.3.1 Patients with Adverse Events, Patients with Serious Adverse Events, Patients with Fatal Adverse Events and Patients with Adverse Events Causing Treatment Discontinuation

3.3.2 Patients with Adverse Events by MedDRA System Organ Class

3.3.3 Patients with Adverse Events by MedDRA System Organ Class and Preferred Term

3.4 Incidence Adverse Events

3.4.1 Number of Adverse Events, Serious Adverse Events, Fatal Adverse Events and Number of Adverse Events Causing Treatment Discontinuation

3.4.2 Number of Adverse Events by MedDRA System Organ Class

3.4.3 Number of Adverse Events by MedDRA System Organ Class and Preferred Term

3.5 Incidence Adverse Events Divided by Total Exposure to Treatment

3.5.1 Number of Adverse Events, Serious Adverse Events, Fatal Adverse Events and Number of Adverse Events Causing Treatment Discontinuation

3.5.2 Number of Adverse Events by MedDRA System Organ Class

3.5.3 Number of Adverse Events by MedDRA System Organ Class and Preferred Term

3.6 Reasons for Seriousness for Serious Adverse Events

3.7 Serious Adverse Events

3.7.1 Patients with Adverse Events by MedDRA System Organ Class and Preferred Term

3.7.2 Number of Adverse Events by MedDRA System Organ Class and Preferred Term

Psoriatic Arthritis

1 Baseline Characteristics– All Patients and Broken Down by Early Termination

- 1.1 Age
- 1.2 Gender
- 1.3 Disease Duration Before Inclusion
- 1.4 Anti-TNF use Before Inclusion
 - 1.4.1 Anti-TNF Naïve / Experienced
 - 1.4.2 Types of Anti-TNF use Before Inclusion
- 1.5 Physician's Assessment of Disease Activity
- 1.6 Clinical Examination
 - 1.6.1 Joint Assessment (tender joints count, swollen joints count)
 - 1.6.2 Inflammatory Parameters (CRP, ESR)
 - 1.6.3 Physical Function (HAQ %)
 - 1.6.4 BSA with Psoriasis
 - 1.6.5 Patient's Numerical Rating Scale for Oligoarticular PsA Patients
 - 1.6.6 Physician's Numerical Rating Scale for Oligoarticular PsA Patients
- 1.7 Concomitant Medication
 - 1.7.1 Concomitant Steroids
 - 1.7.2 Concomitant NSAIDs
 - 1.7.3 Concomitant Immunomodulators
 - 1.7.4 Number of DMARDs Used
 - 1.7.5 Frequency of Use of Each Type of DMARD
 - 1.7.6 Combination of Types of DMARD Used
- 1.8 Study Duration
- 1.9 Results of the Tests

2 Follow-up Data

- 2.1 Treatment Duration
 - 2.1.1 Treatment Duration
 - 2.1.2 Treatment Duration Category
 - 2.1.3 Treatment Duration Broken Down by Year of Start Treatment
 - 2.1.4 Treatment Duration Broken Down by DAS28 Category at Window 2 (Month 6)
- 2.2 Physician's Assessment of Disease Activity
 - 2.2.1 Physician's Assessment of Disease Activity in Each Window
 - 2.2.2 Physician's Assessment of Disease Activity - Difference from Baseline
- 2.3 Clinical Examination
 - 2.3.1 Joint Assessment (tender joints count, swollen joints count) in Each Window
 - 2.3.2 Joint Assessment (tender joints count, swollen joints count) – Difference from Baseline
 - 2.3.3 Inflammatory Parameters (CRP, ESR) in Each Window
 - 2.3.4 Inflammatory Parameters (CRP, ESR) – Difference from Baseline
 - 2.3.5 Physical Function (HAQ %) in Each Window
 - 2.3.6 Physical Function (HAQ %) – Difference from Baseline
 - 2.3.7 Physical Function (HAQ %) - Number of Patients with >7.33% Reduction from Baseline
 - 2.3.8 DAS28 in Each Window
 - 2.3.9 DAS28 Category – Difference From Baseline
 - 2.3.10 DAS28 Category in Each Window
 - 2.3.11 BSA with Psoriasis in Each Window
 - 2.3.12 BSA with Psoriasis - Shift from Baseline
 - 2.3.13 Patient's Numerical Rating Scale for Oligoarticular PsA Patients in Each Window

- 2.3.14 Patient's Numerical Rating Scale for Oligoarticular PsA Patients - Difference from Baseline
- 2.3.15 Physician's Numerical Rating Scale for Oligoarticular PsA Patients in Each Window
- 2.3.16 Physician's Numerical Rating Scale for Oligoarticular PsA Patients - Difference from Baseline

3 Adverse Events

- 3.1 Adverse Events
 - 3.1.1 Patients with Adverse Events, Patients with Serious Adverse Events, Patients with Fatal Adverse Events and Patients with Adverse Events Causing Treatment Discontinuation
 - 3.1.2 Patients with Adverse Events by MedDRA System Organ Class
 - 3.1.3 Patients with Adverse Events by MedDRA System Organ Class and Preferred Term
- 3.2 Adverse Events per Year
 - 3.2.1 Patients with Adverse Events, Patients with Serious Adverse Events, Patients with Fatal Adverse Events and Patients with Adverse Events Causing Treatment Discontinuation
 - 3.2.2 Patients with Adverse Events by MedDRA System Organ Class
 - 3.2.3 Patients with Adverse Events by MedDRA System Organ Class and Preferred Term
- 3.3 Adverse Events by Cumulative Yearly Period
 - 3.3.1 Patients with Adverse Events, Patients with Serious Adverse Events, Patients with Fatal Adverse Events and Patients with Adverse Events Causing Treatment Discontinuation
 - 3.3.2 Patients with Adverse Events by MedDRA System Organ Class
 - 3.3.3 Patients with Adverse Events by MedDRA System Organ Class and Preferred Term
- 3.4 Incidence Adverse Events
 - 3.4.1 Number of Adverse Events, Serious Adverse Events, Fatal Adverse Events and Number of Adverse Events Causing Treatment Discontinuation
 - 3.4.2 Number of Adverse Events by MedDRA System Organ Class
 - 3.4.3 Number of Adverse Events by MedDRA System Organ Class and Preferred Term
- 3.5 Incidence Adverse Events Divided by Total Exposure to Treatment
 - 3.5.1 Number of Adverse Events, Serious Adverse Events, Fatal Adverse Events and Number of Adverse Events Causing Treatment Discontinuation
 - 3.5.2 Number of Adverse Events by MedDRA System Organ Class
 - 3.5.3 Number of Adverse Events by MedDRA System Organ Class and Preferred Term
- 3.6 Reasons for Seriousness for Serious Adverse Events
- 3.7 Serious Adverse Events
 - 3.7.1 Patients with Adverse Events by MedDRA System Organ Class and Preferred Term
 - 3.7.2 Number of Adverse Events by MedDRA System Organ Class and Preferred Term

Ankylosing Spondylitis

1 Baseline Characteristics– All Patients and Broken Down by Early Termination

- 1.1 Age
- 1.2 Gender
- 1.3 Disease Duration Before Inclusion
- 1.4 Anti-TNF use Before Inclusion
 - 1.4.1 Anti-TNF Naïve / Experienced
 - 1.4.2 Types of Anti-TNF use Before Inclusion
- 1.5 Physician's Assessment of Disease Activity
- 1.6 Clinical Examination
 - 1.6.1 Joint Assessment (tender joints count, swollen joints count)
 - 1.6.2 Inflammatory Parameters (CRP, ESR)
 - 1.6.3 Physical Function (HAQ %)
 - 1.6.4 Bath Ankylosing Spondylitis Disease Activity Index (BASDAI)
- 1.7 Concomitant Medication
 - 1.7.1 Concomitant Steroids
 - 1.7.2 Concomitant NSAIDs
 - 1.7.3 Concomitant Immunomodulators
 - 1.7.4 Number of DMARDs Used
 - 1.7.5 Frequency of Use of Each Type of DMARD
 - 1.7.6 Combination of Types of DMARD Used
- 1.8 Study Duration
- 1.9 Results of the Tests

2 Follow-up Data

- 2.1 Treatment Duration
 - 2.1.1 Treatment Duration
 - 2.1.2 Treatment Duration Category
 - 2.1.3 Treatment Duration Broken Down by Year of Start Treatment
 - 2.1.4 Treatment Duration Broken Down by DAS28 Category at Window 2 (Month 6)
- 2.2 Physician's Assessment of Disease Activity
 - 2.2.1 Physician's Assessment of Disease Activity in Each Window
 - 2.2.2 Physician's Assessment of Disease Activity - Difference from Baseline
- 2.3 Clinical Examination
 - 2.3.1 Joint Assessment (tender joints count, swollen joints count) in Each Window
 - 2.3.2 Joint Assessment (tender joints count, swollen joints count) – Difference from Baseline
 - 2.3.3 Inflammatory Parameters (CRP, ESR) in Each Window
 - 2.3.4 Inflammatory Parameters (CRP, ESR) – Difference from Baseline
 - 2.3.5 Physical Function (HAQ %) in Each Window
 - 2.3.6 Physical Function (HAQ %) – Difference from Baseline
 - 2.3.7 Physical Function (HAQ %) - Number of Patients with >7.33% Reduction from Baseline
 - 2.3.8 DAS28 in Each Window
 - 2.3.9 DAS28 Category – Difference From Baseline
 - 2.3.10 DAS28 Category in Each Window
 - 2.3.11 Bath Ankylosing Spondylitis Disease Activity Index (BASDAI) in Each Window
 - 2.3.12 Bath Ankylosing Spondylitis Disease Activity Index (BASDAI) - Difference from Baseline
 - 2.3.13 Bath Ankylosing Spondylitis Disease Activity Index (BASDAI) - Responder

3 Adverse Events

